#### Intervention

The custom MCP blocking orthosis was made of a 6-mm-thick thermoplastic material that extends from the palm over the MCP joint and includes a ring around the proximal phalanx. It is designed to block the MCP joint in flexion of 10°-20° while allowing full range of motion of the proximal and distal interphalangeal joints. The RME orthosis was fabricated from 3.2-mm-thick thermoplastic material with the affected finger positioned at an extension of approximately 10°-20° relative to the adjacent fingers. Both orthoses were fabricated in about 20-30 minutes, with the RME orthosis taking slightly less time than the MCP orthosis. If necessary, modifications were made to alleviate the discomfort associated with the orthosis, such as placing a strap over the proximal phalanx in patients with edema. Patients were instructed to remove the orthosis only for hygiene.

### Measurements

Demographic information obtained during the pre-treatment assessment included: age, gender, affected finger, dominant hand, duration of symptoms and occupation. The primary outcome measures were performed twice, before and after treatment at six weeks. The primary outcomes were pain and function. Pain intensity was assessed using a numeric pain rating scale (NPRS). Functional status was assessed with the Disabilities of Arm, Shoulder, and Hand Questionnaire (DASH).

Satisfaction with the orthosis was a secondary outcome of this study. The Quebec Assistive Technology User Satisfaction Evaluation (Quest 2.0) was used to assess patients' satisfaction with their orthoses. Of the 12-item Quest instrument, 8 items evaluate the characteristics of the assistive device in terms of dimensions (size), weight, adjustments, safety, durability, ease of use, comfort, and effectiveness. The remaining four items evaluate service, including service delivery, repairs and service of the assistive device, professionalism of service, and follow-up service. The instrument also included an assessment of satisfaction with the device on a five-point scale. In the final section, participants were asked to select the

three most important items related to the assistive device from 12 short satisfaction statements.

Since emotional status is related to disability in trigger finger patients, the Beck Depression Scale (BDS) and the Beck Anxiety Scale (BAS) are used to determine the severity of depression and anxiety, respectively. A higher score indicates more severe depression or anxiety.

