### Study design

This study was conducted to compare the efficacy of metacarpophalangeal (MCP)-blocking orthosis with relative motion extension (RME) orthosis in patients with trigger finger between June 2021 and March 2022 at a university hospital. The study was approved by the University Institutional Research Ethics Board. Patients were informed about the study and provided written informed consent before enrolment. The inclusion criteria were patients diagnosed with Stage 1-3 trigger finger, A1 pulley triggering and aged between 18 and 60 years. We excluded patients with trigger thumb, multiple trigger fingers on one hand, neurological disorders, rheumatologic diseases, pregnancy, and patients who had received a steroid injection in the affected finger within the previous six months or who had previously undergone trigger release surgery.

Power analysis was performed using G\*Power 3.1 to test the difference between pretreatment and post-treatment means with a two-tailed test, (primary outcome was pain and function ), and an alpha of 0.05. A total sample of 30 participants was required to achieve a power of 0.90.

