# Statistical analysis

Descriptive analyses were presented using means and standard deviations and using medians and interquartile ranges (IQR) for the non-normally distributed and ordinal variables (using frequency tables for the ordinal variables). The normal distribution of the continuous variables was tested using visual (histogram and probability plots) and analytical methods (Shapiro-Wilk test). DASH, BDS and BAS scores was normally distributed; the NRPS and Quebec scores, age, gender, affected hand and finger, symptom duration were not normally distributed. The Student T test was used for normally distributed data and two-tailed Wilcoxon signed rank test was used for non-normally distributed data to compare pretreatment and post-treatment results. The Mann-Whitney U test was used to analyse the difference between two groups. The significance level was set at p < 0.05.

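### Pain and function are both primary with no adjustment, order or success rule; if either alone can show superiority, the false-claim rate is about 7–10%, not 5%

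*Combined protocol and SAP*

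**What the plan says.** The Study design section gives a comparative aim: the study was "conducted to compare the efficacy of metacarpophalangeal (MCP)-blocking orthosis with relative motion extension (RME) orthosis in patients with trigger finger". Its power paragraph names pain and function together ("primary outcome was pain and function") with a single two-tailed alpha of 0.05. That alpha belongs to a calculation set up "to test the difference between pretreatment and post-treatment means with a two-tailed test".

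The Measurements section repeats that "The primary outcomes were pain and function" and assigns one instrument to each, NPRS to pain and DASH to function. Neither is called the lead outcome.

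The Statistical analysis section uses a t test or a Wilcoxon signed rank test for change from before to after treatment. For the comparison of the orthoses it says only that "The Mann-Whitney U test was used to analyse the difference between two groups". It closes with "The significance level was set at p < 0.05". It does not list the outcomes compared between groups. It gives no multiplicity adjustment, no testing order and no rule on whether one or both primaries must be significant.

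**The concern.** With two primaries and no rule, the text lets one orthosis be called better on whichever of pain or function reaches 0.05. That gives chance two opportunities to produce a positive trial, each at the full 5%. The planned total is only 30, so a single outcome just under the threshold could carry the whole comparative conclusion.

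The power paragraph does not close the gap. Its alpha concerns change over time, so it sets no between-group rule and does not divide the error between the two outcomes.

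**Working it through.** **Inputs from the documents.** Two primary outcomes (Study design; Measurements). Two-sided testing with alpha 0.05 in the power paragraph (Study design) and a threshold of 0.05 (Statistical analysis). Mann-Whitney as the only between-group test (Statistical analysis). Total of 30 (Study design), allocated 1:1 (Study sample), so 30/2 = 15 per arm.

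**Assumptions.** The documents do not give the correlation between NPRS and DASH, so 0, 0.5, 0.7 and 0.9 are shown. That each primary is compared between groups at 0.05 is inferred from the comparative aim. A false claim in either direction counts.

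**The plan's own figure.** The total of 30 for 0.90 power cannot be reproduced, because no effect size or SD is given. Solving backwards, it implies a standardised effect of 0.61 for a paired test on all 30, 0.90 for a paired test within one arm of 15, or 1.23 for a t test of 15 against 15. None of the error rates below depends on this.

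**Step 1: normal theory.** With both null hypotheses true,

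P(either) = 0.05 + 0.05 − P(both).

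- Correlation 0: P(both) = 0.05² = 0.0025, so P(either) = 0.10 − 0.0025 = 0.0975.
- Correlation 0.5: 0.10 − 0.0093 = 0.0907.
- Correlation 0.7: 0.10 − 0.0165 = 0.0835.
- Correlation 0.9: 0.10 − 0.0296 = 0.0704.

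Under Holm, a false claim when both nulls are true requires the smaller p-value to be at or below 0.025. That gives 0.0494, 0.0465, 0.0430 and 0.0362.

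**Step 2: the test the plan names.** At 15 per arm the exact Mann-Whitney test at 0.05 rejects when the smaller U is 64 or less (true size 0.0453), and at 0.025 when it is 58 or less (true size 0.0235). At correlation 0 the either-outcome rate is therefore 1 − (1 − 0.0453)² = 0.0885. The table comes from 200,000 simulated trials per correlation. The large-sample rows use tie-corrected p-values without continuity correction, with NPRS rounded to 0–10 (assumed mean 4, SD 2).

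| Rule and version | 0 | 0.5 | 0.7 | 0.9 |
|---|---|---|---|---|
| Either outcome, exact | 8.9% | 8.2% | 7.7% | 6.6% |
| Either outcome, large-sample | 9.6% | 9.1% | 8.4% | 7.3% |
| Holm, exact | 4.6% | 4.4% | 4.1% | 3.5% |
| Holm, large-sample | 4.6% | 4.4% | 4.2% | 3.6% |
| Both required, exact | 0.2% | 0.7% | 1.3% | 2.4% |

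**Step 3: how often the rule changes the answer.** This is the either-outcome rate minus the Holm rate. With the exact test at correlation 0 it is 0.0889 − 0.0463 = 0.0426; at 0.9 it is 0.0663 − 0.0352 = 0.0311. Across both versions, in 3.1% to 5.0% of trials with no true difference an unadjusted test is significant while Holm rejects nothing.

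**Step 4: cost in power.** With normal data and 15 per arm, 0.90 power at 0.05 needs a between-group difference of 1.28 SD (exact) or 1.26 SD (large-sample). At 0.025 the power for those differences is 0.840 and 0.828.

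**The case against.** The arithmetic and the omission are not in dispute. The case against is about framing and remedy.

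- **The inflation depends on two conditions.** Both primaries must be tested between groups at 0.05, and either must be allowed to carry the conclusion. The plan states neither. This stands as a limit on the claim. The comparative aim makes the first condition likely, and the plan's silence on the second is itself the defect.
- **Pain and function could be reported as separate conclusions, each with 5% error.** That reading is open, and whether the two claims need joint control is partly a matter of judgement in a small comparison of two active orthoses. Even so, the chance of at least one false primary claim stays above 5%.
- **The top of the range is generous.** It needs uncorrelated outcomes in the same patients, which is implausible, and the exact test never reaches 9%. For correlations of 0.5 to 0.9 the rate is about 6.6% to 9.1% across methods. This stands, and it lowers the size without removing the problem.
- **Any rule added now is post hoc, including Holm.** This also stands. Holm treats the two outcomes alike and so leaves the least room for choice after seeing results, but it cannot count as pre-specified.
- **The power cost is hypothetical.** The plan's 0.90 is for change over time, and no between-group effect is given. The loss in Step 4 is illustrative.

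**Conclusion.** The concern holds. The plan names two primaries for a comparative aim and applies an unadjusted 0.05 with no success rule, so it permits a superiority claim on either outcome. Read that way, the false-claim rate is about 7–10%, up to nearly twice the stated 5%. The size rests on an either-outcome reading, 15 per arm and an assumed correlation between 0 and 0.9. If both outcomes were required there would be no inflation. The figure covers only the two between-group primary tests; the within-group tests are also unadjusted and are not counted in it. The omission is certain. How the results would be read is not, which makes this a worthwhile improvement of moderate weight.

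**What to change.** In the Statistical analysis section, apply Holm's procedure to the two between-group primary tests: the smaller p-value is tested at 0.025 and, if it passes, the other at 0.05. Base the comparative conclusion on these two tests alone. Keep the before-and-after tests as descriptions of change within each group, and do not let them or the secondary outcomes support a claim that one orthosis is better.

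Report both group differences with 95% confidence intervals, for example the Hodges-Lehmann shift to match Mann-Whitney. Label the intervals as unadjusted, and do not use them to claim superiority where Holm does not reject.

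The study is described as already conducted, so state plainly that the rule was added after the analysis. Requiring both outcomes, or testing in a fixed order, would also control the error, but neither should be chosen once the results are known.

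The cost is a short addition to the text and no new data. Power at the first Holm step falls from 0.90 to about 0.83–0.84 for the illustrative effects in Step 4. Requiring both outcomes is not free either: with 1.28 SD on each, its power is 0.81, 0.83 and 0.87 at correlations 0, 0.5 and 0.9. With that effect on one outcome only and correlation 0.5, the rule is met in just 3.7% of trials. Since no rule can now be pre-specified, the main gain is transparent reporting of both outcomes.

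### The between-arm DASH comparison adjusts for neither baseline DASH nor a baseline emotional score, and the role and timing of BDS and BAS are not stated

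*Combined protocol and SAP*

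**What the plan says.** All references are to the combined protocol and SAP.

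- **Primary outcomes (Measurements):** "The primary outcomes were pain and function", with function scored by DASH. On timing: "The primary outcome measures were performed twice, before and after treatment at six weeks".
- **Mood scales (Measurements):** "Since emotional status is related to disability in trigger finger patients, the Beck Depression Scale (BDS) and the Beck Anxiety Scale (BAS) are used" to grade depression and anxiety. No timing is given, and neither scale is ranked as an outcome. The only secondary outcome named is satisfaction: "Satisfaction with the orthosis was a secondary outcome of this study".
- **Statistical analysis:** BDS and BAS appear once, in the statement on distributions: "DASH, BDS and BAS scores was normally distributed". Pre-to-post comparisons follow a generic rule: "The Student T test was used for normally distributed data and two-tailed Wilcoxon signed rank test was used for non-normally distributed data". Between arms: "The Mann-Whitney U test was used to analyse the difference between two groups". The section does not say whether that test uses six-week scores or changes. No covariate, regression or stratified analysis is described.
- **Study design and Study sample:** 30 patients in total, allocated 1:1, with no stratification described.

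**The concern.** The study exists to compare two orthoses, so the between-arm test carries the main conclusion. For DASH, the plan has a baseline score in hand and does not adjust for it. It also states that emotional status goes with disability, and then makes no use of emotional status when comparing disability between arms. The reason for collecting the data and the analysis do not connect.

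Two things are at stake. The first is power, because variation in six-week DASH that baseline measurements could explain is left in the error term. The second is chance imbalance. With about 15 patients per arm and no stratification, the arms can easily differ at baseline in something related to DASH, and an unadjusted comparison cannot allow for it.

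**Working it through.** **The plan's own figure.** The stated 30 patients for power 0.90 cannot be reproduced, because no effect size or SD is given. Solved backwards with the noncentral t distribution (two-sided alpha 0.05), it corresponds to a standardised pre-post change of 0.61 (30 patients pooled) or 0.90 (15 in one arm), or to a between-arm difference of 1.23 SD (15 per arm). None of these is stated, so the between-arm effect below is an assumption.

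**Inputs from the document:** total 30, 1:1, hence 15 per arm; alpha 0.05. **Assumed:** true difference 0.9 SD of six-week DASH; correlation of baseline with six-week DASH r = 0.5; partial correlation p of baseline BDS with six-week DASH, given baseline DASH, from 0 to 0.5.

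**Step 1: chance imbalance.** The standardised baseline difference between arms has SD √(2/15) = 0.365. The chance that it exceeds 0.5 SD in either direction is P(|Z| > 0.5/0.365 = 1.37) = 0.17. Its expected absolute size is 0.365 × √(2/π) = 0.29 SD. A gap of 0.5 SD in a covariate with correlation r shifts the unadjusted DASH difference by 0.5 × r: 0.10 SD at r = 0.2, 0.15 at 0.3, 0.25 at 0.5.

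**Step 2: adding baseline DASH.** With k covariates explaining a share R² of the variance, and df = 28 − k, the variance of the arm difference is approximately

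V = (2/15) × (1 − R²) × (df − 1 + k)/(df − 1).

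- No covariate: V = 0.133, SE 0.365, noncentrality 0.9/0.365 = 2.46, power of a t test 0.66. Simulated power of Mann-Whitney is about 0.62.
- Baseline DASH (R² = 0.25): V = 0.133 × 0.75 × 27/26 = 0.104, SE 0.322, noncentrality 2.79, power 0.77.

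**Step 3: adding baseline BDS.** Now V = 0.133 × 0.75 × (1 − p²) × 27/25 = 0.108 × (1 − p²). Relative to Step 2 the ratio is (26/25) × (1 − p²) = 1.04 × (1 − p²).

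| p | Change in variance | Power |
|---|---|---|
| 0 | +4% | 0.75 |
| 0.1 | +3% | 0.75 |
| 0.2 | about 0 | 0.77 |
| 0.3 | −5% | 0.79 |
| 0.4 | −13% | 0.82 |
| 0.5 | −22% | 0.86 |

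Break-even is where 1 − p² = 25/26, that is p = √(1/26) = 0.196. Simulation of the same setting agrees to within about 0.02 in power, and puts the cost at p = 0 at up to about 5% of variance.

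**Step 4: sensitivity to r.** Taking the variance of six-week DASH as 1, adjustment for baseline DASH leaves 1 − r² = 0.91, 0.75 or 0.51 at r = 0.3, 0.5 or 0.7. A change score has variance 2(1 − r) = 1.4, 1.0 or 0.6. At r = 0.5 the change and the six-week score have the same variance, so the 0.62 for Mann-Whitney applies to either reading of the plan.

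**The case against.** The best case against the point is that its emotional-status part is thin. The document says only that emotional status and disability are related. That may be a cross-sectional association, and low mood may partly result from disability. A useful covariate must predict six-week DASH beyond baseline DASH, and the document is silent on that. It does not even establish that BDS was measured before treatment. With 30 patients, a weak second covariate costs a little. All of this stands. Most of the gain comes from baseline DASH, and BDS is a conditional addition.

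It can also be said that a Mann-Whitney test on change scores would already use baseline DASH. It would, by subtraction, but the document does not say that changes were compared, and Step 4 shows that adjustment leaves less variance than the change score at each r considered.

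Two stronger readings are tempting, and the document supports neither.

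- A reader might infer that BDS and BAS are tested as extra outcomes and add p-values at 0.05. No test of them is named and no list of tested outcomes includes them. The sentence on distributions that mentions them also covers age, gender, affected finger and symptom duration, which are not outcomes.
- A reader might infer that the unadjusted comparison is invalid. If allocation was truly random, chance imbalance does not inflate type I error. It affects precision and how this one result reads.

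**Conclusion.** The point holds as a cheap improvement. The between-arm DASH analysis leaves out an adjustment that the plan's own data allow, and the purpose and timing of BDS and BAS need stating.

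Under the assumptions above, power rises from about 0.62 to about 0.77. About 0.04 of that comes from moving to a test based on means (0.62 to 0.66), and about 0.11 from baseline DASH (0.66 to 0.77). Baseline BDS adds about 0.02 to 0.09 more if its partial correlation is 0.3 to 0.5, nothing near 0.2, and a small loss below that. The 17% chance of a baseline gap over 0.5 SD needs only 15 per arm, random allocation and an approximately normal difference in means. The power figures also depend on the 0.9 SD effect and on correlations that the document does not give. They also take DASH as approximately normal, which is what the plan reports.

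**What to change.** 1. State when BDS and BAS were completed and what they are for.
2. Make the between-arm DASH analysis a prespecified linear model (ANCOVA) of six-week DASH on arm and baseline DASH, reporting the adjusted difference with its 95% confidence interval.
3. If BDS was measured before allocation, add it as one further prespecified covariate, with BAS in its place as a sensitivity analysis. Do not enter both in the main model. If neither was measured then, stop at baseline DASH.
4. Never adjust for a six-week BDS or BAS value, which treatment may have affected.
5. Report any change in BDS or BAS descriptively.

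The cost is a few sentences and one or two model terms. No new data are needed for baseline DASH, nor for BDS if a pre-allocation score exists. Each covariate uses one degree of freedom; for BDS the worst case is about 3 to 5% of variance. The plan already reports observed distributions, so if outcomes by arm have been seen, the adjusted model should be presented as added afterwards, beside the Mann-Whitney result.

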# Statistical analysis

Descriptive analyses were presented using means and standard deviations and using medians and interquartile ranges (IQR) for the non-normally distributed and ordinal variables (using frequency tables for the ordinal variables). The normal distribution of the continuous variables was tested using visual (histogram and probability plots) and analytical methods (Shapiro-Wilk test). DASH, BDS and BAS scores was normally distributed; the NRPS and Quebec scores, age, gender, affected hand and finger, symptom duration were not normally distributed. The Student T test was used for normally distributed data and two-tailed Wilcoxon signed rank test was used for non-normally distributed data to compare pretreatment and post-treatment results. The Mann-Whitney U test was used to analyse the difference between two groups. The significance level was set at p < 0.05.

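### The MCP-versus-RME comparison has no specified baseline adjustment, effect estimate or confidence interval, and the score tested is not stated

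*Combined protocol and SAP*

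**What the plan says.** The Study design section states the aim: "This study was conducted to compare the efficacy of metacarpophalangeal (MCP)-blocking orthosis with relative motion extension (RME) orthosis". The Measurements section makes pain (NPRS) and function (DASH) the primary outcomes and adds: "The primary outcome measures were performed twice, before and after treatment at six weeks". A baseline value of each primary outcome is therefore part of the design.

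The Statistical analysis section gives the group comparison one sentence: "The Mann-Whitney U test was used to analyse the difference between two groups". The other tests serve a different contrast. Student's t test is tied to the before/after comparison for normal data, and the "two-tailed Wilcoxon signed rank test was used for non-normally distributed data to compare pretreatment and post-treatment results". Means, SDs, medians and interquartile ranges are mentioned only as descriptive summaries. The decision rule is: "The significance level was set at p < 0.05".

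On distributions, the section reports that "DASH, BDS and BAS scores was normally distributed", while "the NRPS and Quebec scores, age, gender, affected hand and finger, symptom duration were not normally distributed".

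**The concern.** The trial's main question is how far the two orthoses differ, but the only inferential output described for it is a p-value. Three things are missing from that comparison.

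- **The analysis variable.** Testing six-week scores and testing changes from baseline are different analyses and can have quite different power.
- **Any use of baseline as a covariate.** With normal scores, adjusting a six-week score for its own baseline is at least as efficient as either option, apart from the small cost of one degree of freedom.
- **An estimate with an interval.** With about 15 patients per arm, a non-significant result can be misread as equivalence when the data may still be compatible with a large difference. A p-value alone does not show this.

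The plan's own reason for rank methods, non-normality, does not apply to DASH, yet no other between-group test is named for it.

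**Working it through.** **Inputs from the documents.** Total sample 30 and power 0.90 (Study design); 1:1 allocation (Study sample), hence 15 per arm; two-sided 0.05.

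**Inputs assumed, because the documents give none.** True difference 0.8 SD (range 0.5 to 1.1); baseline to six-week correlation r = 0.3, 0.5, 0.7; equal SDs at both visits; no dropout; NPRS scored 0 to 10.

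**The plan's own figure.** The 30 cannot be reproduced, since no effect size, SD or correlation is stated. Solving backwards with the noncentral t distribution, 90% power implies a paired standardised effect of 0.61 with 30 patients, 0.90 if each arm of 15 is tested alone, or 1.23 SD if read as a two-group comparison. The stated contrast is before versus after treatment, so none of these supplies a planned MCP-RME difference.

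**Variance, relative to the six-week variance.** The factor is 1 for the six-week score, 2(1−r) for change and 1−r² for ANCOVA. At r = 0.3/0.5/0.7, change gives 1.4/1.0/0.6 and ANCOVA gives 0.91/0.75/0.51. Because 2(1−r) − (1−r²) = (1−r)², ANCOVA's factor never exceeds that of change.

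**Power of the corresponding t tests.** The noncentrality is 0.8 × √(15/2) ÷ √factor, which is 2.19 for six-week scores. Power is 0.562 for six-week scores, 0.432/0.562/0.779 for change, and 0.600/0.684/0.841 for ANCOVA (27 df).

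**Power with the rank test, normal scores, 0.8 SD** (simulation, 20,000 trials per cell):

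| Analysis | r = 0.3 | r = 0.5 | r = 0.7 |
|---|---|---|---|
| t test, six-week | 0.567 | 0.562 | 0.558 |
| Mann-Whitney, six-week | 0.526 | 0.524 | 0.521 |
| Mann-Whitney, change | 0.405 | 0.528 | 0.739 |
| ANCOVA | 0.589 | 0.669 | 0.824 |

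- ANCOVA minus Mann-Whitney six-week: 6.3/14.5/30.3 points. About 4 of these come from using ranks (0.567 − 0.526 = 0.041 at r = 0.3) and the rest from omitting baseline.
- ANCOVA minus Mann-Whitney change: 18.4/14.1/8.5 points.
- At 0.5 SD the gains are 3/9/20 (six-week) and 9/9/8 (change). At 1.1 SD they are 5/11/18 and 20/11/3.
- At lower r (0.1 and 0.2, 0.8 SD), six-week Mann-Whitney has 0.52 against ANCOVA 0.55 and 0.56, so the gain falls to 3 to 4 points. Change scores have only 0.32 and 0.35.
- The equality of the two Mann-Whitney versions at r = 0.5 needs equal SDs. With a baseline SD 0.7 or 1.3 times the six-week SD, change-score power is about 0.63 or 0.40, against 0.52.

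**NPRS on assumed 0 to 10 scales, shift of 0.8 SD on the underlying normal scale, r = 0.3/0.5/0.7:**

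| Scale | Mann-Whitney six-week | Raw ANCOVA | Rank ANCOVA |
|---|---|---|---|
| Mild floor | 0.521/0.520/0.519 | 0.570/0.647/0.786 | 0.553/0.624/0.761 |
| Half the lower arm at 0 | 0.497/0.491/0.498 | 0.523/0.583/0.717 | 0.524/0.581/0.715 |
| Skewness 2.0 | 0.509/0.509/0.498 | 0.495/0.558/0.667 | 0.539/0.607/0.733 |

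In the skewed case at r = 0.3, raw ANCOVA is about 1 point below Mann-Whitney, and rank ANCOVA is 3 points above it.

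**Validity.** Over the normal and the three bounded scales, simulated type I error is 0.043–0.049 for Mann-Whitney, 0.044–0.051 for ANCOVA and 0.049–0.053 for rank ANCOVA.

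**Intervals.** The unadjusted 95% half-width is t(0.975, 28 df) × √(2/15) = 0.75 SD. With ANCOVA it is t(0.975, 27 df) × √(2/15 × (1−r²)) = 0.71/0.65/0.54 SD. On the three bounded NPRS scales the ANCOVA t interval covers 0.940–0.953.

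**The case against.** Mann-Whitney is a valid test, and preferring ANCOVA is a choice between valid analyses. That stands, and it rules out several stronger readings.

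- **A reader might infer that baseline was ignored.** The text does not establish this. If changes were compared, baseline entered by subtraction, and it also enters the before/after tests. What can be said is that no baseline adjustment is specified for the group comparison.
- **A reader might infer inflated false positives.** The simulated error rates show none.
- **A reader might infer that this trial lost a known amount of power, or reached a wrong conclusion.** The documents give no effect size, SD or correlation. Across the effect sizes and correlations of 0.3 to 0.7 examined with normal scores, the gain runs from 3 to 30 points. Nothing shows that a conclusion changed.
- **Raw-score ANCOVA may not help NPRS.** This stands for a strongly skewed score with low correlation. The documents say only that NPRS is non-normal, not how skewed it is, so raw ANCOVA is neither ruled out nor assured of a gain.
- **DASH means and SDs may allow an unadjusted interval.** This is true if they are reported by arm, which is not stated. They would not yield the adjusted one.
- **The study appears complete.** The past tense and the reported normality results suggest so, and an adjusted analysis added now cannot be presented as pre-specified. Several p-values for one outcome would also invite selective reporting, so the remedy should stay small.

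The missing estimate and interval, and the unstated score, depend on none of the assumed inputs.

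**Conclusion.** The point holds as a recommended improvement, not as an error that invalidates the analysis. With high confidence, the Statistical analysis section specifies no baseline adjustment, estimate or interval for the trial's main comparison and does not identify the score tested. On its own, the unstated score would be only a missing detail.

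The efficiency claim is conditional. It holds for DASH, given the stated normality, with gains of roughly 6 to 30 points over six-week Mann-Whitney and 9 to 18 over change-score Mann-Whitney under the 0.8 SD assumptions. The gain over six-week scores shrinks as the correlation falls. For NPRS the direction depends on the unknown skew, and raw ANCOVA may gain nothing at a correlation around 0.3 or below.

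**What to change.** 1. For DASH and for NPRS, analyse the six-week score by ANCOVA on arm and baseline score. Report the adjusted MCP-minus-RME difference in scale points with a 95% t interval.
2. For NPRS, take the p-value from a single rank-based adjusted test: rank ANCOVA, in which pooled ranks of the six-week score are regressed on pooled ranks of baseline and the residuals compared between arms. State that this p-value carries the NPRS test, since it and the t interval can disagree at the margin.
3. Keep the Mann-Whitney result beside these, state whether it used six-week or change scores, and give its Hodges-Lehmann difference with a 95% confidence interval.
4. Label the adjusted analysis post hoc if it is added after results were seen.

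The cost is one degree of freedom per model (28 to 27 with 30 patients), a residual check and a little extra analysis. No new data, visits or patients are needed.
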